4.3.3 Subjects on Dose Level 2 (6.25 mg/Placebo Daily)

Four weeks following escalation from dose level 1 to 2, subjects will return to clinic for a clinical evaluation. During that visit, there will be two options:

- Increase to dose level 3, *or*
- Maintain at the current dose level if dose escalation is considered inadvisable by the investigator.

Individuals on dose level 2 who are unable to tolerate dose escalation to level 3 have the option to return in 2 weeks, where there will be another attempt at dose escalation. If at that time, dose escalation is not considered advisable by the investigator, then subjects will remain on dose level 2 for the duration of the study. For these individuals, dose level 2 will be considered the fixed maintenance dose.

4.4 **Maintenance Period**

At the completion of the up-titration period, subjects will enter the maintenance phase of the study which will last 24 months from the first dose of study drug. For the purposes of this study, the initial maintenance visit will be synonymous with the “end of up-titration” visit. Subjects will enter the maintenance phase receiving the highest dose of study medication that was tolerated in the up-titration phase. This may be dose level 2 or 3.

During the maintenance period, study visits will be scheduled on 90, 180, 365, 540, and 730 days. These study visits may occur within +/- 10 business days of the calculated visit day. Additional visits may be scheduled by the investigator, as appropriate, based on clinical indication. The study CRA/CRN will follow-up with a telephone call in between clinic visits, as outlined below.

4.5 **Follow-up Visits**

Study participants will be asked to return their pill kits on Day 90 for a pill count, refill of the medication, and clinical evaluation; patient reported symptoms will be accessed via a standardized Symptom Log (see study web page on the COG website). For the Day 90 visit only, the patient has the option to do an in-person visit or a phone follow up, depending on their ability to easily return to the clinic.

Subsequent return clinic visits will occur on Days 180, 365, 540 and 730 following randomization. The following parameters will be assessed according to the study observations (see [Section 7.1](#)).

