Because of randomization, we expect no difference between the expected values of LV T-D z-scores at t0 between the treatment groups. However, we will evaluate the success of the randomization by examining between-group differences in demographic and clinical characteristics (i.e. age at anthracycline exposure, chest radiation, time from treatment), study site, as well as the mean LV T and D z-scores at baseline. If imbalance is evident, our analysis will take into account the covariates with significant imbalance.

Low dose carvedilol will be considered effective if the 1-df test in the linear model is significant and the expected LV T-D z-score is lower for placebo at follow-up

time points, indicating the effectiveness of low-dose carvedilol in preserving LV T-D.

In addition to unadjusted analyses which are appropriate under the randomization principle, adjusted analysis will also be performed. Significantly imbalanced covariates and covariates known to be prognostic for HF, such as age at anthracycline exposure, chest irradiation, and time from completion of treatment, will be incorporated in the longitudinal models before including and testing the time by treatment group interaction.

To address potential noncompliance, we will also conduct an as-treated analysis, considering patients' actual treatment uptake. Instead of the treatment indicator (placebo or carvedilol), we will include adherence rate, i.e. 0 for placebo and a number between 0 and 1 for carvedilol determined by pill count, in the linear mixed effects model. Time-specific adherence rate and the overall adherence rate will be considered. If carvedilol is effective, we may expect to see an increase in LV T-D z-score and a greater difference in slope with increasing adherence rate.

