9.3.4 Subjective Safety and Tolerability Measures

Treatment adherence. Patients will self-report adherence in the study questionnaires. Compliance will also be measured by pill counts performed every 3 months. The number of pills taken out of the total prescribed in a 3-month period will be modeled as a random effects binomial regression model.¹²⁶ The binomial rates from 8 time points (month 3 to 24) will be modeled as unstructured mean model with 7 indicator variables as well as polynomial models over time. The random-intercept and the random intercept and slope models will be considered. The significance of the time indicators or parameters by treatment interaction will be evaluated for treatment difference in compliance.

Voluntary withdrawals will be examined at the end of the study by comparing the percent of withdrawals between the treatment groups using a chi-square test or Fisher's exact test.

Patient reported symptoms. The outcomes will be scored as a 5-point Likert-type scale (0 to 4) in response to questions on how much the patients are bothered by certain symptoms. The questionnaire will be administered at Days 0, 14, 42 and 90, and every three months after Day 90, for a total of eleven time points. The responses will be treated as normally distributed, as ordinal or dichotomized variable, and we will apply the linear mixed effects model or generalized linear mixed effects model methods to compare changes between treatment groups. Because of additional time points available, in addition to the unstructured mean model, we will also fit piecewise models with join point at 6 months, considering linear and curvilinear trajectories between 6 m and 24 m time points.

Aim 1.2.2: To examine the modifying effects of demographic, clinical, and molecular characteristics on both efficacy and safety markers.

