As the primary aim of this trial is to examine the main effects of low-dose carvedilol on LV-TD z-score, we will examine the modifying effects of demographic, clinical, and molecular characteristics as exploratory analysis. Even if time by treatment interaction (main treatment effect) is not significant, examining the modifying effects of covariates may reveal subgroups that respond differently to carvedilol. A three-way interaction of time by treatment by modifying variable will be included in the longitudinal model containing a two-way time by treatment group interaction. Modifying effects will be considered statistically significant if the three-way interaction is significant. The covariates of interest are described below.

A. Patient demographics

The following variables are known to affect HF risk and LV T-D.

Attained age – continuous, time-varying variable.

Body mass index (BMI) – continuous, time-varying variable. It will also be grouped into ordinal categories: underweight (<19), normal weight (19-24), overweight (25-29), obese (30-39), morbidly obese (40+).

Cardiovascular disease – coronary artery disease (angina, acute myocardial infarction, coronary artery bypass graft surgery [CABG], percutaneous coronary intervention), ventricular or atrial arrhythmias, cerebrovascular disease, congenital heart lesions.

CV risk factors – Hypertension, dyslipidemia, diabetes, renal insufficiency, chronic lung disease, thyroid disorder, smoking history (includes smoking status, and if quit, date of cessation). All CV risk factors will be recorded as dichotomous variables (present/absent), with recording of date of onset.

Family history of cardiovascular disease – dichotomous (yes/no), constant over the study period. Outcomes of interest will include: sudden cardiac death, conduction system disease, cardiomyopathy, and coronary artery disease (CAD). For the CAD, we will also examine the frequency of the following classifications: 0 = no direct blood relatives (parents, siblings) with CAD; 1 = one or more with CAD at age ≥ 55 years for male relatives or ≥ 65 years for female relatives; 2 = one or more with CAD at age less than 55 years for male relatives or less than 65 years for female relatives.

B. Clinical treatment characteristics.

The following variables are known to influence HF risk among childhood cancer survivors.

Chest radiation – continuous, time-invariant. We will also dichotomize per the stratification factor for randomization.

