Voluntary withdrawals: We assume that the proportion of patients in the placebo arm who will withdraw voluntarily by 24 months is 20% (10%/year); of note, this is less than the assumed overall attrition rate of 15%/year because attrition could occur due to other reasons such as toxicities, cancer recurrence, etc. With 125 patients in each arm at baseline, using Type I error=0.05, the study will have 80% power to detect a >15% absolute difference in the voluntary withdrawal rates between the two study arms.

WITH AMENDMENT #4:

Adverse events: We assume the rate of Grade 2-4 toxicities in the placebo group to be low, at 5%. At the end of the study, assuming 56 individuals remaining in each arm (19% attrition/year from the 91/arm at baseline), the study will have at least 80% power to detect an adverse event rate of 24.7% in the carvedilol group based on Fisher's exact test and Type I error=0.05.

Adherence to therapy: We will examine the difference in adherence rates by comparing the percent adherence by treatment group. With 91 study participants at baseline per arm, assuming a constant adherence rate of 90% in the placebo group, a between-measurement correlation of 0.6, 19% yearly attrition, and 2-sided alternative, there will be 80% power to detect an adherence rate of $\leq 70\%$ in the carvedilol group.

Voluntary withdrawals: We assume that the proportion of patients in the placebo arm who will withdraw voluntarily by 24 months is 26% (13%/year); of note, this is less than the assumed overall attrition rate of 19%/year because attrition could occur due to other reasons such as toxicities, cancer recurrence, etc. With 91 patients in each arm at baseline, using Type I error=0.05, the study will have 80% power to detect a >21% absolute difference in the voluntary withdrawal rates between the two study arms.

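### Adherence is tested in 9.3.4 only by the time-by-treatment interaction, but 9.4 powers a difference in percent adherence between arms; a gap stable from month 3 would go undetected

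*Combined protocol and SAP*

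**What the plan says.** Section 9.3.4 (Treatment adherence) fits a random-effects binomial regression to pills taken out of pills prescribed in each three-month period: "The binomial rates from 8 time points (month 3 to 24) will be modeled as unstructured mean model with 7 indicator variables", with polynomial time models as alternatives. The inferential step is one sentence: "The significance of the time indicators or parameters by treatment interaction will be evaluated for treatment difference in compliance". It mentions no group main effect, no contrast averaged over periods and no joint test.

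Section 9.4 (Adherence to therapy) describes a different comparison: "We will examine the difference in adherence rates by comparing the percent adherence by treatment group". The Amendment #4 inputs begin "With 91 study participants at baseline per arm, assuming a constant adherence rate of 90% in the placebo group" and continue with a between-measurement correlation of 0.6, 19% yearly attrition and a two-sided alternative. The stated result is 80% power for a carvedilol rate of 70% or lower. The activation text has the same form, with 125 per arm, 15% attrition and 75% on carvedilol. Neither paragraph names a test statistic or an alpha.

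**The concern.** For LV T-D the time-by-treatment interaction is a sound test of treatment. Section 9.3.1 relies on a common starting point, "we expect no difference between the expected values of LV T-D z-scores at t0 between the treatment groups", so any treatment effect must appear as divergence. The text for Aim 1.2.2 accordingly equates the two: "Even if time by treatment interaction (main treatment effect) is not significant".

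Adherence has no such anchor. There is no pre-treatment value, and the first modelled period ends at month 3, when patients have been on study drug for three months. Randomization does not make the arms equal there. A gap that exists by month 3 and then holds lies wholly in the group term, which 9.3.4 does not test.

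An early gap is plausible. The second titration visit is at Day 42, and under section 4.4, "Subjects will enter the maintenance phase receiving the highest dose of study medication that was tolerated in the up-titration phase". Intolerance may therefore already have affected pill-taking by the month-3 count.

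Adherence is a tolerability measure under secondary aim 1.2.1. An analyst who follows 9.3.4 could report no treatment difference in compliance when carvedilol adherence is clearly lower throughout.

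**Working it through.** **Inputs.** From 9.4 with Amendment #4: 91 per arm, placebo 90%, carvedilol 70%, correlation 0.6, attrition 19% per year, two-sided. From 9.3.4: 8 periods. Alpha 0.05 is an assumption, since the adherence paragraph gives none. Attrition leaves 91 × (1 − 0.38) = 56.4 per arm at month 24, matching the 56 in the adverse-event paragraph.

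**The plan's 80%.** No single consistent method gave it to within 2 points in both versions.
- One time point, 56 per arm: pooled null SE √(2 × 0.8 × 0.2/56) = 0.0756; alternative SE √((0.09 + 0.21)/56) = 0.0732; (0.20 − 1.96 × 0.0756)/0.0732 = 0.71, so power is 76% (Fisher exact 69%).
- One time point, 60 per arm (compounded attrition): 79%.
- Joint 8-df test of the arm differences at all periods: 86%.
- Difference averaged over the 8 periods: 98%.
- Activation version (125 per arm, 90% v 75%): 75% at one time point with 88 per arm, 78% joint, 97% averaged.

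The stated 80% lies within these ranges, and 9.4 does not say which contrast it used. The point below does not depend on the answer.

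**The named test under a stable gap.** Let d(k) be the arm difference in period k. The 7-df interaction tests d(k) − d(1) = 0 for k = 2 to 8. With 90% v 70% throughout, d(k) = 0.20 and every contrast is 0.20 − 0.20 = 0. On the logit scale, ln(0.9/0.1) − ln(0.7/0.3) = 2.197 − 0.847 = 1.350 in every period, so every contrast is again zero. The noncentrality is 0 and the rejection probability equals alpha, whatever the size of the gap or the sample. The slope-by-treatment term is zero for the same reason.

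**The arm difference averaged over periods.** With complete data its variance is [0.9 × 0.1 + 0.7 × 0.3] × [1 + 7 × 0.6]/8 ÷ 91 = 0.30 × 0.65/91 = 0.00214, SE 0.0463. Then 0.20/0.0463 = 4.32, and 4.32 − 1.96 = 2.36 gives 99% power. With attrition spread over the two years it is 98.4%. With only 56 per arm throughout, SE = √(0.195/56) = 0.0590 and power is 92%.

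**Simulation.** 3,000 trials per scenario; binary adherence per period, exchangeable correlation 0.6, linear dropout, GEE with robust variance. Percentage of trials rejecting:

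| Scenario (placebo 90%) | 1-df interaction | 7-df interaction | Averaged difference | Joint 2-df (group + slope) |
|---|---|---|---|---|
| Null, 90% in both arms | 5.0 | 3.7 | 4.8 | – |
| Carvedilol 70% from month 3 | 5.2 | 4.6 | 98.3 | 96.9 |
| 80% at month 3, then 70% | 28.4 | 37.7 | 97.6 | – |
| Linear decline, 90% at month 0 to 70% at month 24 | 95.8 | 73.1 | 72.6 | 95.5 |

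In the decline scenario the interaction result depends on the estimator: 56% on 1 df from per-patient slopes, and 60.6% on 7 df in completers only. For the stable gap, averaged-difference power is 97% to 99% for correlations from 0.5 to 0.8.

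A pill-count version closer to 9.3.4 (180 pills per period assumed, logit-normal patient and period effects, within-arm correlation about 0.61, 2,000 trials) gave 5.7%, 5.9% and 100% for the stable gap, in the order 1-df, 7-df, averaged. A separate 1,000-trial run of the stable gap gave 5.5% for the slope, 4.3% for the 7-df interaction and 98.4% for the averaged difference.

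**The case against.** **The group comparison is already in the plan, in 9.4.** It is, as a statement of intent, but with no test attached. The analytic plan in 9.3 is where tests are assigned, and it assigns another one. By contrast, adverse events and voluntary withdrawals are compared by arm in 9.3 and powered the same way in 9.4.

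**A model without a group main effect would let the interaction pick up a stable gap.** That is true in part. Such a model, with the arms sharing an intercept, rejected in 49% (linear) and 39% (7-df) of simulated binary trials, and in 94% and 87% with pill-count fractions under assumed variances. But 9.3.4 does not specify such a model, and it would impose equal adherence at a post-randomization visit, which nothing in the design justifies.

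**The stable gap is inferred.** This stands as a limit. Section 9.4 calls only the placebo rate constant. If carvedilol adherence falls gradually, the interaction has power and the averaged difference reaches only 73%.

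**The simulations leave out the rule in 8.1(h) that removes patients below 50% adherence in a 90-day period.** With that rule in the pill-count version, the observed gap shrank from 20 points at month 3 to about 6 at month 24. The interaction still rejected in only 7% (1-df) and 12% (7-df) of trials. So the 97% to 99% for the averaged difference is somewhat idealised, but the interaction is not rescued.

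**Tolerability is also judged on adverse events, withdrawals and symptoms, and no decision rule uses adherence.** Also true. It limits the consequence but does not make the named test suit the stated purpose.

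**Conclusion.** The concern holds. The test named in 9.3.4 does not address the quantity powered in 9.4. For a gap of 90% v 70% that is stable from month 3, it rejects about 5% of the time, against about 98% for the averaged arm difference. If half the gap is present at month 3 and the rest opens by the next period, the named test has 28% to 38% power against 97.6%.

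This rests on a model that includes a group term, on alpha 0.05, and on a gap largely present by month 3. The last is the natural reading of a single carvedilol rate in 9.4 but is not stated there. Under gradual decline the named test performs adequately or well, depending on the estimator. Because the time course is unknown in advance, the adherence test should not depend on it. The consequence is confined to a secondary tolerability measure, and the LV T-D analysis is untouched.

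**What to change.** In 9.3.4, name the treatment effect averaged over the 8 periods as the test of a treatment difference in adherence, state that the model includes a group term, and keep the time-by-treatment interaction as a secondary assessment of trend. If the team wants one test that does not depend on the time course, use the joint 2-df test of group and linear interaction: 97% power for the stable gap and 96% for the gradual decline at the plan's inputs.

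In 9.4, tie the 80% power statement to whichever test is named; the method and alpha can be added in the same clause.

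The cost is one sentence in 9.3.4 and one clause in 9.4, with no new data and no change to the sample size.

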10.6.1 Measurement of Blood Pressure, Heart Rate, Body Weight and Height

Blood pressure, heart rate, body height and weight will be measured prior to enrollment, as well as at each subsequent clinic visit whenever possible. The same method should be used to measure blood pressure throughout the study. All measurements should be made on the same extremity using appropriate cuff size and equipment. Diastolic blood pressure will be measured at the disappearance of

Kortkoff sounds – Phase V. If possible, measurements will be taken by the same staff member at each visit.

Sitting/supine blood pressure and heart rate should be measured after the subject has been sitting quietly for at least 5 minutes. Body height and weight should be measured without shoes, using the same equipment at each visit whenever possible.

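### BMI is tested as an effect modifier using on-treatment values that the drug may change; the modifier should be baseline BMI

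*Combined protocol and SAP*

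**What the plan says.** The effect-modification plan for Aim 1.2.2 is in Section 9.3.4. Its status is explicit: "we will examine the modifying effects of demographic, clinical, and molecular characteristics as exploratory analysis". The method is equally clear: "A three-way interaction of time by treatment by modifying variable will be included in the longitudinal model", with the decision rule "Modifying effects will be considered statistically significant if the three-way interaction is significant".

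The demographic modifiers are introduced by "The following variables are known to affect HF risk and LV T-D". The list then includes "Attained age – continuous, time-varying variable" and describes BMI as a "continuous, time-varying variable. It will also be grouped into ordinal categories", of which there are five, with cuts at 19, 25, 30 and 40. No version of BMI fixed at baseline is stated. By contrast, chest radiation and age at anthracycline exposure are time-invariant, and family history and genotype are constant over the study.

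Section 10.6.1 gives the timing of the measurements: "Blood pressure, heart rate, body height and weight will be measured prior to enrollment, as well as at each subsequent clinic visit whenever possible". Section 6.1.2 lists weight gain among the occasional toxicities of carvedilol (4-20% of patients).

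**The concern.** Taken together, these sections describe a variable that the drug may change and that is said to affect the outcome, and they use its on-treatment values to define who benefits. A patient whose BMI goes from 29 to 30 during treatment moves from the overweight to the obese group. If the drug contributed to that change, the subgroup is partly an outcome.

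Two things follow. First, within levels of current BMI the arms are no longer comparable by randomization, so a three-way interaction may reflect how patients responded rather than what they were like beforehand. Second, current BMI at 12 or 24 months is not available when treatment is chosen. Section 2.7 hypothesizes a subgroup that benefits most with least risk, and Section 9.3.4 allows the search to go ahead even if the main effect is not significant. A modifier that cannot be known in advance does not serve that purpose.

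**Working it through.** **Plan figures.** The documents give no figure for the effect-modification analysis, so there is none to reproduce. Table 4 in Section 9.4 serves to check the longitudinal set-up. The detectable 24-month difference is (z₀.₉₇₅ + z₀.₈₀) × √V / (c·d). Here c is the normalized linear contrast over five visits, d runs from 0 to 1, and V = 2 Σᵢⱼ cᵢcⱼSᵢⱼ/√(NᵢNⱼ). S is compound symmetric with SD 1, and N at t years is 91 × (1 − 0.19)^t. For correlations 0.6, 0.7, 0.8 and 0.9 this gives 0.380, 0.333, 0.278 and 0.208, against 0.38, 0.34, 0.28 and 0.21 in the table. They agree to within 0.01.

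**Simulation of the planned three-way model.**
- From the documents: 91 per arm, five visits over two years, 19% attrition per year, correlation 0.7, a placebo slope of −0.2 z per year and a direct treatment effect of 0.2 z per year (Section 9.4).
- Assumed, not in the documents: baseline BMI SD 5 (centred), a drug shift in BMI of +1 or +2 units over two years, SD of BMI change 1 to 3, a BMI effect of 0 to 0.05 z per unit, and an unmeasured factor that drives both BMI change and LV T-D slope by 0 to 0.2 z per year per SD.
- Analysis: exchangeable GEE with robust standard errors, 1,500 runs per cell. In truth baseline BMI modifies nothing.

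Each cell shows the mean three-way coefficient, its rejection rate at 5%, and the mean time by treatment slope.

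| Assumed scenario | Time-varying BMI | Baseline BMI |
|---|---|---|
| A: drug +1, BMI has no effect on LV T-D | −0.0003; 7.1%; 0.203 | 0.0001; 6.9%; 0.198 |
| B: drug +1, 0.02 z per unit | −0.0001; 6.1%; 0.203 | −0.0003; 6.5%; 0.209 |
| B2: drug +2, 0.05 z per unit | −0.0001; 6.5%; 0.203 | 0.0002; 5.8%; 0.250 |
| C: drug +1, link 0.1 in treated arm, SD of change 1 | 0.0026; 6.8%; 0.195 | 0.0000; 5.9%; 0.202 |
| C2: link 0.2 in treated arm, SD 2 | 0.0075; 9.8%; 0.180 | 0.0001; 6.0%; 0.202 |
| C3: link 0.2 in treated arm, SD 3 | 0.0090; 13.7%; 0.173 | 0.0000; 6.7%; 0.205 |
| D: link 0.2 in both arms, SD 2 | 0.0002; 6.7%; 0.178 | 0.0001; 6.2%; 0.199 |

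The simulation error of a 5% rate is √(0.05 × 0.95/1,500) = 0.6 percentage points. Rates slightly above 5% with either form are expected from robust standard errors at this sample size.

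**Reading the table.**
- In A, B and B2 the drug changes BMI but nothing else links BMI change to response. The three-way test behaves as it does with baseline BMI.
- In B2 the total slope effect is 0.20 + 0.05 × (2/2) = 0.25 z per year. Baseline BMI recovers 0.250. Time-varying BMI gives 0.203, so (0.250 − 0.203)/0.250 = 19% of the total effect is conditioned away.
- In C2 and C3 a false three-way effect appears. In C the difference from baseline BMI is within simulation error.
- In D the three-way test is unharmed, but the slope falls from a true 0.20 to 0.178, or 11%.

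**Age and latency.** Attained age is age at randomization plus elapsed time t, so t × treatment × attained age = t × treatment × baseline age + t² × treatment. The only consequence is an added time-squared by treatment component. The same algebra holds for latency from radiation.

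**The case against.** The strongest reply is that weight gain plus a BMI effect on LV T-D is not enough to distort the three-way test, as scenarios A to B2 show. A false interaction needs BMI change to track response in the treated arm, which the documents neither state nor quantify. That stands: bias is possible, not shown.

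The toxicity table gives neither a placebo rate nor an amount of weight gained, so it does not establish a BMI difference between arms in this trial. If only 4-20% of patients gained, a mean shift of +1 unit would need 1/0.20 = 5 to 1/0.04 = 25 units in each affected patient. The simulated shifts are therefore generous on that reading. This also stands, and it limits what can be said about size.

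A reader might infer that part of the projected 0.4 z primary effect is lost. The documents do not support this. The primary analysis in Section 9.3.1 is the 1-df time by group test, which contains no BMI term, and BMI is not among the covariates named there for the adjusted analysis.

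A reader might also put attained age and radiation latency under the same criticism. Treatment cannot alter either, so they do not share the problem.

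Finally, Section 9.3.4 also plans to relate the modifiers to the outcomes in order to confirm known relationships. Time-varying BMI is a reasonable form for that separate purpose and need not be dropped there.

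None of this supplies a reason to prefer current over baseline BMI as the modifier.

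**Conclusion.** The point holds for BMI alone and is of low severity. As written, the plan conditions on a post-randomization variable that its own toxicity table says the drug may change and that it says affects LV T-D. The resulting subgroups can be partly defined by treatment, and they do not answer who should be treated.

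The size cannot be obtained from the documents. Under the assumptions above, the false-positive rate of the BMI interaction ranged from no detectable increase to 13.7%, and the treatment slope inside that model could lose up to about a fifth of the total effect. The slope loss matters only if that coefficient is read as the treatment effect. To say that the subgroup results are biased would go too far, and to extend the point to the whole modifier list would too. The cardiovascular risk factors, recorded with date of onset, could raise a similar question if updated after baseline, but the text does not say they will be. The efficacy conclusion is not touched.

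**What to change.** In Section 9.3.4, define the BMI modifier in the time by treatment by modifier model as BMI at baseline, both continuous and in the stated categories. Keep time-varying BMI for description, or for the separate analysis of its relationship with the outcomes.

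Optionally, enter age and latency from radiation as their values at randomization. The only gain is to keep the time-squared by treatment component out of those models, since Section 9.3.1 already tests curvature separately.

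The cost is wording only. Height and weight are already measured before enrollment, and no visit, sample size or primary analysis changes.

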3.2 Patient Eligibility Criteria

Important note: The eligibility criteria listed below are interpreted literally and cannot be waived (per COG policy posted 5/11/01). All clinical and laboratory data required for determining eligibility of a patient enrolled on this trial must be available in the patient's medical/research record which will serve as the source document for verification at the time of audit.

See [Section 7.1](#) for required studies to be obtained prior to starting protocol therapy.

INCLUSION CRITERIA**3.2.1 Current Weight for Males and Females**

3.2.1.1 Males and Females must weigh ≥ 40 Kg.

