3.2.2 Age at Cancer Diagnosis

Patient must have had a cancer diagnosis < 22 years of age, irrespective of current age.

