3.2.4 Timing from Cancer Treatment to Study Entry

Patient must have completed cancer treatment ≥ 2 years prior to study enrollment.

EXCLUSION CRITERIA**3.2.5 Cardiac Treatment or Conditions**

3.2.5.1 Receiving treatment for cardiomyopathy or heart failure.

3.2.5.2 Ejection fraction of $< 50\%$ (by radionuclide angiogram or echocardiogram) or shortening fraction of $< 25\%$ (by echocardiogram).

Note: for instances where both are reported, and one is below the threshold, the site will have the option to re-measure it centrally at the core lab.

3.2.5.3 Uncorrected primary obstructive or severe regurgitative valvular disease:

- Nondilated (restrictive); or
- Hypertrophic cardiomyopathy; or
- Significant systemic ventricular outflow obstruction.

3.2.5.4 Sustained or symptomatic ventricular dysrhythmias uncontrolled with drug therapy or implantable device.

3.2.5.5 Significant conduction defects (i.e. second or third degree atrio-ventricular block or sick sinus syndrome).

3.2.5.6 Bradycardia: heart rate < 50 Beats per minute (BPM).

3.2.5.7 Use of an investigational drug or beta adrenergic blockers, including metoprolol, sotalol, within 30 days of enrollment.

3.2.5.8 History of drug sensitivity or allergic reaction to alpha or beta-blockers.

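### The exploratory BMI modifier in Aim 1.2.2 is not standardised for age or sex although minors of at least 40 kg can enter, so some adolescents may be misbanded and the BMI interaction may be confounded with age

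*Combined protocol and SAP*

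**What the plan says.** Under Aim 1.2.2 in Section 9.3, the list of patient demographics defines the modifier as "Body mass index (BMI) – continuous, time-varying variable. It will also be grouped into ordinal categories". The categories are "underweight (<19), normal weight (19-24), overweight (25-29), obese (30-39), morbidly obese (40" and above). The raw continuous form comes first and the bands are a second coding. Neither refers to age or sex.

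Age is a separate entry in the same list: "Attained age – continuous, time-varying variable". The model for each candidate is described in the singular: "A three-way interaction of time by treatment by modifying variable will be included in the longitudinal model". A modifier is declared significant if that three-way term is significant. The text does not say that the BMI term is fitted together with an age term. The status of the work is clear: "we will examine the modifying effects of demographic, clinical, and molecular characteristics as exploratory analysis".

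On who can enter, Section 3.2.1 says "Males and Females must weigh ≥ 40 Kg", Section 3.2.2 says "Patient must have had a cancer diagnosis < 22 years of age, irrespective of current age", and Section 3.2.4 says "Patient must have completed cancer treatment ≥ 2 years prior to study enrollment". None of these sets a minimum current age. Section 3.2.9.1 provides for consent by parents or guardians, and the table of contents lists a youth information sheet as Appendix III, so minors are expected.

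**The concern.** A fixed BMI band means the same thing for two people only if a given BMI means the same thing for both. In participants who are still growing, BMI depends on age and sex as well as on build. That premise is general and is not taken from the documents. If it holds, two things follow.

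First, the lowest band can mix thin adults with adolescents whose BMI is unremarkable for their age. Second, raw BMI in either coding partly tracks age among the younger participants. The plan itself lists both age and BMI among variables that affect heart failure risk and LV T-D. A significant BMI by time by treatment term could then reflect modification by age, or a real BMI effect could be blurred.

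BMI is also time-varying. A growing participant can cross a band boundary during the two years through growth alone, along the same time axis as the slope under study.

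What is at stake is the reading of one exploratory modifier. The question is still a reasonable one to ask: the dose levels in Section 4.3 are set in mg and not per kg, and Section 2.7 hypothesises a subgroup with the best balance of benefit and risk.

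**Working it through.** The plan gives no power, sample size or error rate for the BMI modifier, so there is no stated figure to reproduce. What can be checked is which admitted participants fall below the lowest cut-off.

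**Inputs.** Lowest cut-off: BMI 19 (Section 9.3, Aim 1.2.2). Minimum weight: 40 kg (Section 3.2.1). Heights and weights above the floor are assumed, because the documents give no height or BMI distribution.

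**Formula.** BMI = weight / height², so BMI is below 19 when height exceeds √(weight / 19).

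| Weight | Height above which BMI is below 19 |
|---|---|
| 40 kg | √(40/19) = 1.451 m |
| 45 kg | √(45/19) = 1.539 m |
| 50 kg | √(50/19) = 1.622 m |
| 55 kg | √(55/19) = 1.701 m |

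Read the other way, with weight at BMI 19 = 19 × height²:

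| Assumed height | BMI at 40 kg | Admitted weights coded underweight |
|---|---|---|
| 150 cm | 17.8 | 40 to 42.8 kg |
| 155 cm | 16.6 | 40 to 45.6 kg |
| 160 cm | 15.6 | 40 to 48.6 kg |
| 165 cm | 14.7 | 40 to 51.7 kg |

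The lightest admitted participants therefore fall in the lowest band over a range of plausible heights.

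**Movement between bands.** Take an assumed participant of 155 cm and 45 kg: 45 / 1.55² = 18.7, underweight. At 160 cm and 50 kg the figure is 50 / 1.60² = 19.5, normal weight. The category changes although the participant has only grown.

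**What the arithmetic does not show.** It does not show that any of these people is normal weight for age. That needs a growth reference, and the documents contain none. A 40 kg adult of 160 cm also has BMI 15.6, and the lowest band is meant to catch that person.

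**Notation.** BMI comes from measured height and weight (Section 10.6.1), so non-integer values are usual. Read literally, values between 24 and 25, 29 and 30, and 39 and 40 have no category. A BMI of 24.7 is overweight if rounded and normal weight if truncated.

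**The case against.** The strongest reply is that this is a second coding of one covariate in an exploratory analysis. BMI is listed first as continuous, and attained age has its own entry directly above it, so modification by age will be examined and can be read beside the BMI result. The only age figure for a comparable population, the planning cohort in Section 9.4, is a median of 24.2 years at evaluation, which points to many adults. The weight floor and the two years off treatment keep out the smallest and many of the youngest children. The gaps between bands are ordinary whole-number shorthand.

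Most of this stands, and it limits the point. It does not remove it. Continuous BMI without standardisation has the same dependence on age as the bands. Two separate models, one for age and one for BMI, do not separate the two effects as one joint model can. The planning cohort is not this trial. The gaps are a notation matter only.

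A reader might infer that normal-weight adolescents in general are coded underweight, or that the lowest band will consist of the youngest participants. The documents support neither: there is no growth reference and no age distribution. A reader might also assume that 10% to 30% of the 182 participants are minors and count 18 to 55 people as wrongly banded (0.10 × 182 = 18.2; 0.30 × 182 = 54.6). That share has no basis in the documents, and the count covers every assumed minor, not those whose category would change under another reference.

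**Conclusion.** The point holds in a limited form. The plan uses BMI without age or sex standardisation in both codings, minors from 40 kg are eligible, and no joint adjustment of the BMI interaction for age is stated. Some adolescents with BMI below 19 may be coded underweight when they are not underweight for their age, and the BMI interaction may be confounded with age.

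This rests on two assumptions: that BMI depends on age among growing participants, and that enough minors enrol for it to matter. The size of the effect is unknown, because the documents give no age, height or BMI distribution for those enrolled. Calling the bands adult bands is an inference from their being the same at all ages; the plan does not use the word.

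The primary one-degree-of-freedom slope test, the sample size and the type I error are unaffected. This is a low-cost improvement, not a flaw in the design.

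**What to change.** **Categorical coding.** Assign participants under 20 to the BMI groups by age- and sex-specific percentiles from a reference named in the SAP. Keep the fixed bands for older participants, written without gaps: below 19, 19 to <25, 25 to <30, 30 to <40, and 40 or more. State which reference applies to someone who turns 20 on study.

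**Continuous coding.** Keep raw BMI on one scale for everyone. Add the age by time by treatment term, with its lower-order terms, to the BMI by time by treatment model, and report the two interactions together. State whether age in that term is baseline or attained age: attained age equals baseline age plus time, so its product with time brings in a squared-time term. Do not put z-scores for those under 20 and raw BMI for older participants into one variable. One coefficient would then mix standard-deviation units with kg/m², and a participant turning 20 on study would jump scale.

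**Cost.** A few lines of SAP text and a reference table. Date of birth and gender are already collected (Section 10.7), and height and weight are measured at clinic visits whenever possible (Section 10.6.1). The downsides are that the categories use two references by age, and that the continuous model carries extra age terms in an analysis that is already exploratory.
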